4.4 Screening for Eligibility

It is anticipated that participants will be recruited from PFDN Clinical Site practices. Women with MUI will be offered the full range of treatment options consistent with routine practice including expectant management, pelvic floor muscle therapy, behavioral therapy, medication, and possibly surgery. Patients who are considered candidates for either Botox A injection or mid-urethral sling by their physician will be offered participation in MUSA.

Subjects will be identified as MUSA candidates by their physician. Subjects will be approached by study personnel consistent with local IRB requirements. Enrollment will occur after written and/or verbal consent. If the participant accepts participation in MUSA, the UDI will be administered to confirm at least moderate bother from both SUI and UUI and the coordinator will confirm documentation of SUI by either CST or UDE within the past 18 months, and UI symptoms for at least 3 months. She will be instructed on how to complete the voiding diary.

To address the issue of overactive bladder medication use, these subjects will be required to have a washout of 3 weeks prior to completing the voiding diary. The anticholinergic medication with the longest half-life currently on the market is Vesicare with a half-life of 45-68 hours. Therefore, by 1 week there should be negligible amounts in the bloodstream and by 2 weeks the drug would be completely out of the system. Therefore, 3 weeks should be adequate time for washout and this time period is consistent with prior PFDN studies (ABC trial,³⁵ ESTEEM,⁴⁹ ROSETTA³³). In addition, because we are highly interested in what happens to OAB outcomes, subjects will need to remain off overactive bladder medication for the 6 month duration of the study to allow accurate assessment of these symptoms following treatment (See statistical analysis plan for details). Subjects who take overactive bladder medication during the study period will be considered as having “additional treatment”. Every effort will be made to schedule the patient’s surgery within 2 months from enrollment (see Section 4.6, Appointment scheduling below).

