4.3 Exclusion Criteria

1. Anterior or apical compartment prolapse at or beyond the hymen (≥ 0 on POPQ), regardless if patient is symptomatic
 - a. Women with anterior or apical prolapse above the hymen (<0) who do not report vaginal bulge symptoms will be eligible
2. Planned concomitant surgery for anterior vaginal wall or apical prolapse ≥ 0
 - b. Women undergoing only rectocele repair or other repair unrelated to anterior or apical compartment are eligible
3. Women undergoing hysterectomy for any indication will be excluded
4. Active pelvic organ malignancy
5. Age <21 years
6. Pregnant or plans for future pregnancy in next 6 months, or within 12 months post-partum
7. Post-void residual >150 cc on 2 occasions within the past 6 months, or current catheter use
8. Participation in other trial that may influence results of this study
9. Unevaluated hematuria
10. Prior sling, synthetic mesh for prolapse, implanted nerve stimulator for urinary incontinence
Women with known Burch or Marshall-Marchetti-Krantz (MMK) are excluded.
11. Spinal cord injury or advanced/severe neurologic conditions including Multiple Sclerosis, Parkinsons, Myasthenia Gravis, Charcot-Marie-Tooth
12. Women on overactive bladder medication/therapy will be eligible after 3 week wash-out period
13. Non-ambulatory
14. History of serious adverse reaction to synthetic mesh
15. Not able to complete study assessments per clinician judgment, or not available for 6 month follow-up
16. Diagnosis of and/or history of bladder pain or chronic pelvic pain
17. Women who had intravesical Botox injection within the past 12 months
18. Women who have undergone anterior or apical pelvic organ prolapse repair within the past 6 months

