5.3 Patient Management and Follow-Up

5.3.1 Baseline Procedures

In addition to information collected to determine eligibility and standardized questionnaires, the following information will be obtained for all randomized patients by chart review or patient report:

- a. Demographic information: age, race, ethnicity, insurance status, education
- b. Medical history: vaginal parity, comorbidities, height, weight, prior pelvic surgeries, medications, estrogen status, previous treatments for pelvic floor disorders
- c. Social history: tobacco use
- d. Pelvic, rectal exam, and neurological examination will be done if indicated. POP-Q, post-void residual, urinary cough stress test will be documented.
- e. Standardized urodynamic evaluation (UDE) will be performed before study interventions – there are no specific UDE parameters that determine eligibility for this trial beyond diagnosis of SUI defined by a positive CST or UDE. Small retrospective studies suggest that UDE parameters may be helpful in predicting outcomes after surgery in women with MUI and were predictors of failure in ESTEEM.^{23,96} Therefore, patients in MUSA will undergo UDE testing, primarily to allow evaluation of variables that may predict clinical outcome. If patients have already undergone UDE prior to enrollment, results performed within 18 months of enrollment will be allowed if studies meet MUSA standards. For those women who have not, UDE will be performed at baseline.
- f. Patient-reported outcomes and questionnaires – includes UDI, IIQ, EQ5D, PGI-I, PGI-S, OAB-q, OAB-SAT-q, PISQ-IR, SF-36, PGSC.

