5.3.2 Postoperative Visits and Procedures

Patients will undergo clinical and PRO assessments at 2-weeks, 3 months, and 6 months postoperatively (See **Table 9**). The primary outcome will be at 6 months.

Table 9: Timeline of Visits, Events, and Data Collection

	Screening	Baseline	Procedure (Botox or Sling) ^{‡, **}	1-2 Week Visit ^{**}	Telephone Call	3 Month Visit	Botox reinjection ^{‡, **}	1-2 Week Visit ^{**}	Telephone Call	6 Month Visit [†]
Window	1-4 w	1-4 w			1w before 3m visit	2 w pre – 4 w post			1w before 6m visit	2 w pre – 4 w post
Consent	X									
Coordinator visit	X	X		X	X	X		X	X	X
Hx/PE	X	X				X				X
Urodynamics**		X								
Medication and other treatment audit	X	X				X				X
Preg test~**			X				X			
Urine dip~**	X	X	X	X		X	X	X		X
PVR	X	X		X		X		X		X
Adverse Events			X	X		X	X	X		X
PGSC						X				X
UDI		X				X				X
Bladder diary		X			Diary reminder	X			Diary reminder	X
PRO/Questionnaires Varies by milestone.		X		X		X		X		X

[†] primary outcome visit

* all subjects will undergo a post-op visit for PVR/urine dip 2 weeks after Botox A or sling procedure

[‡] standard of care visit

** must be done in clinic

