4.6 Study Flow Chart of Assessments and Evaluations

MUSA Statistical Analysis Plan

· · · · · · · · · · · · · · · · · · ·		1						1	1		
§ OAB-q	Х	Х			Х		Х	Х	Х		
§ IIQ	Х	Х			Х		Х	Х	Х		
§ PISQ	Х	Х			Х		Х	Х	Х		
§ EQ-5D	Х	Х		Х	X	Х	Х	Х	Х		
§ SF-36/ SF- 6D	Х	Х		Х	Х	Х	Х	Х	Х		
§ PGI-S	Х	Х			X		Х	Х	Х		
§ Lost Productivity / Costs				Х	X	Х	X	X	X		
§ OAB-SAT-q					Х		Х	Х	Х		
§ PGI-I					Х		Х	Х	Х		
§ PGSC					Х		Х	Х	Х		
Final Status										Х	
Adverse Events											Х
Serious AE											Х
Protocol Viol. /Deviation											Х
CISC/PVR – Patient Reported											Х
Additional Therapies											Х
Additional Office Visits											Х

*Repeat baseline if not randomized and treatment not initiated within 90 days of the date UDI completed as part of the initial baseline visit.

[†] Performed in clinic only. MUS procedure urine dip collected per usual clinical practice.

§ Patient Reported Outcomes

Note; extended follow-up begins after the 6m visit.

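### The documents disagree on whether the baseline UDI comes before or after the OAB-drug washout, and no passage requires it to be off drug

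*Protocol*

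**What the plan says.** Passages that put the UDI before the washout, or leave that open:

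- Protocol 4.4: "If the participant accepts participation in MUSA, the UDI will be administered to confirm at least moderate bother from both SUI and UUI". Diary instruction follows. The paragraph on OAB medication then sets the timed rule: "these subjects will be required to have a washout of 3 weeks prior to completing the voiding diary". The UDI is not mentioned there.
- SAP 4.6 chart: the UDI row is marked at Screen/Consent and Repeat Baseline and is empty at Baseline/Eligibility. The bladder diary row is marked at Baseline/Eligibility.

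Passages that put the UDI at baseline:

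- Protocol Table 9 ("Timeline of Visits, Events, and Data Collection"): UDI under Baseline with the diary, and nothing under Screening.
- Protocol 5.3.1(f), under baseline procedures: "Patient-reported outcomes and questionnaires – includes UDI, IIQ, EQ5D". Protocol 4.6 also gives the patient-reported outcomes at baseline, 3 and 6 months.
- The footnote to the SAP chart dates the repeat-baseline rule from the UDI: "within 90 days of the date UDI completed as part of the initial baseline visit".

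General rules on medication:

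- Protocol 4.3, exclusion 12: "Women on overactive bladder medication/therapy will be eligible after 3 week wash-out period". This makes washout a condition of eligibility but does not place the UDI relative to it.
- Protocol 4.4, on follow-up: "subjects will need to remain off overactive bladder medication for the 6 month duration of the study". The stated reason is accurate assessment of OAB symptoms.

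**The concern.** The pre-treatment UDI has four uses. It decides inclusions 1 and 2. It is the starting value of the primary change score. It is the covariate in the primary model. It also supplies the two items that classify a woman as stress-predominant, urgency-predominant or balanced, which is the only pre-planned subgroup (SAP 7.9).

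If it is completed on OAB medication and the 6-month UDI off it, her change score carries the effect of stopping the drug as well as the effect of treatment. The protocol's reason for an off-drug follow-up applies equally to the baseline, yet no passage applies it there. Sites that work from 4.4 and sites that work from Table 9 could also collect baselines under different conditions.

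**Working it through.** **1. The plan's own figure.** Inputs from Protocol 6.1.1 and SAP 6 and 7.8: difference 26, SD 46.5, two-sided alpha 0.05, power 90%, 5% discontinuation. A two-sample t calculation gives 68.2, so 69 evaluable per arm; 69/0.95 = 72.6, so 73 per arm and 146 in total. Power with 69 per arm is 90.3% at 26 points and 82.2% at 23 points. The plan's figures reproduce, and the point does not depend on them.

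**2. One response category on the UDI.** SAP 9.2 scores the irritative subscale as the mean of six items (0 to 3) times 100/3, and the total as the sum of three subscales. With all six items answered, one category on one item is (1/6) × (100/3) = 5.6 points on the total.

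**3. Eligibility and MUI type.** Inclusions 1 and 2 need at least moderate bother on both items, so each item is 2 or 3 and there are four eligible profiles. Suppose the drug lowers the urgency item by one category and leaves the stress item alone (assumed):

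| Off drug (urgency, stress) | Class | On drug | Result |
|---|---|---|---|
| 3, 3 | balanced | 2, 3 | stress-predominant |
| 3, 2 | urgency-predominant | 2, 2 | balanced |
| 2, 3 | stress-predominant | 1, 3 | fails inclusion 1 |
| 2, 2 | balanced | 1, 2 | fails inclusion 1 |

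In all four cases a single category changes either her class or her eligibility.

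**4. Within-arm change.** If a share p of women has a baseline lowered by d points, mean improvement in each arm is understated by p × d. Neither p nor d is in the documents. For assumed p of 10% to 50% and d of 10 to 35, the range runs from 0.10 × 10 = 1.0 to 0.50 × 35 = 17.5 points. The upper end is extreme: one category on all six irritative items is only 33.3 points.

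**5. The arm contrast.** The baseline precedes randomisation, so p and d are equal between arms in expectation and the expected bias is zero.

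**6. Power.** The on-drug shift adds variance v = p(1−p)d² to the baseline. Table 6 gives ESTEEM SDs of 43 (baseline), 55 (change) and 46 (change model). If the whole reduction from 55 to 46 is credited to the baseline, the slope of follow-up on baseline is 1 − √((55² − 46²)/43²) = 0.30. At p = 0.5 and d = 35, v = 306. The residual SD rises from 46.5 to 46.75 and power is 90.0%. Over the whole range, power is 90.0% to 90.3%. Adding v in full to 46.5² is a crude bound and gives 86.3% to 90.2%.

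**7. MID and responder work (SAP 9.5.3).** The anchor-based MID is a difference in mean UDI change between two anchor categories. An on-drug shift cancels if the share of such women is the same in both categories, and not otherwise. The distribution-based MID uses the baseline SD. With the ESTEEM value it is 0.5 × 43 = 21.5; at the extreme in step 6 it would be 0.5 × √(43² + 306) = 23.2. Responder percentages take the shift directly, because each woman's change is compared with a fixed threshold.

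**The case against.** The strongest reply is that more passages place the UDI at baseline than at screening, and that Protocol 4.4 can be read as an eligibility check followed by a separate baseline UDI. Protocol 4.5 collects questionnaires after the diary has been reviewed, and exclusion 12 requires washout before a woman is eligible at all. This stands as far as it goes: the documents do not settle on an on-drug baseline. But none of these passages says the UDI follows washout, and the SAP chart has no second pre-treatment UDI except at Repeat Baseline. That repeat replaces the first UDI, but it is triggered by delay and not by medication.

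The effect may also be small. Inclusion 7 selects women with an inadequate response, intolerance or a contraindication. Protocol 2.3.2 describes the drug benefit as modest and discontinuation as high. One sling trial in Table 2, in a different population, had 14% preoperative anticholinergic use. At 14%, a one-item effect gives 0.14 × 5.6 = 0.8 points and a three-item effect 0.14 × 16.7 = 2.3 points. This is fair, and no group figure should be presented as an estimate. The changes in class and eligibility in step 3 need only one category.

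Nor is off-drug follow-up guaranteed. The rule covers 6 months, SAP 7.4 keeps mITT data after off-study treatment, and additional treatment is allowed after 6 months.

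**Conclusion.** The conflict is real and worth resolving. Under Protocol 4.4 and the SAP chart, a woman on OAB medication would have an on-drug baseline UDI; under Table 9 and the other baseline passages she might not. No passage requires an off-drug baseline.

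A reader might infer that the plan fixes an on-drug baseline for the primary outcome, or that the primary comparison is therefore biased. The documents support neither. The placement is contradictory rather than settled, the expected bias in the randomised 6-month contrast is zero, and power stays within 0.3 percentage points of plan under covariate adjustment (about 4 points lower in the crude bound).

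What is exposed is eligibility on inclusion 1, who falls into each MUI-type class, within-arm change, responder percentages and, less certainly, the MID estimates. Comparisons within an MUI class remain randomised, but membership of the class changes meaning. The individual scale is 5.6 points per category per irritative item. The group shift is unknown, and the 1.0 to 17.5 point range in step 4 rests wholly on assumed p and d.

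**What to change.** Reconcile Protocol 4.3 (exclusion 12), Protocol 4.4, Table 9, and the SAP 4.6 chart and its footnote. State that the UDI used for inclusions 1 and 2, the change score, the covariate and MUI type is completed after the washout and before randomisation, with the diary at the baseline visit. State that any earlier UDI is a pre-screen only. The length of the washout is not at issue here.

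Flag women whose only pre-treatment UDI was completed on drug. As a sensitivity analysis, repeat the MUI-type, within-arm, and MID and responder summaries without them. Dropping them from the primary comparison is not needed, since no arm bias is expected and sample would be lost. If enrolment has closed, as the past tense in SAP 7.7 suggests, the flag and the sensitivity analysis are the parts that can still be applied.

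The cost is wording in both documents and one 19-item questionnaire moved to, or repeated at, an existing visit. Eligibility would be confirmed later for some medicated women.

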4.5 Baseline Visit

At the baseline visit, the voiding diary will be reviewed to ensure that entries are clear and interpretable. If the first baseline voiding diary is not acceptable, the subject will be allowed one more attempt. If the second baseline voiding diary is not acceptable, the subject will not be eligible for the trial.

Once eligibility is confirmed, pre-treatment information will be obtained including:

- Demographics – age, race/ethnicity, education level
- Medical history – prior urinary incontinence procedures and treatments, prior pelvic surgeries, comorbidities, smoking, medications
- Physical examination – Body mass index, pelvic organ prolapse quantification (POPQ)
- Questionnaires – self-administered

4.6 Appointment Scheduling and Randomization

Once patients are enrolled and randomized, the intervention (either Botox A or mid-urethral sling) should be scheduled within 8 weeks from randomization. If a participant is randomized but does not undergo the intervention within 8 weeks, the patient can be retained in the study at the investigator’s discretion until the planned intervention is scheduled, with the planned intervention date serving as Time 0 for calculating windows for follow up visits and phone calls. If surgery is rescheduled but does not occur, then the last

planned date of intervention will be Time 0. If the participant decides against the intervention but later changes her mind, the date of the intervention that did occur will be Time 0.

Postoperatively, all subjects will return and/or be contacted for visits at 2 weeks, 3 months, and 6 months. All subjects will return for a clinic visit at 2 weeks after Botox A or mid-urethral sling intervention to check PVR. PROs will be administered at baseline, 3 months, and 6 months post-intervention. (See Assessment Table 9).

5. DESCRIPTION OF STUDY INTERVENTIONS

5.1 Mid-urethral Sling Procedure

In MUSA, we plan to allow retropubic as well as transobturator full length slings. This is based on the findings of the TOMUS and Barber's equivalence trials in which these approaches demonstrated equivalence for improving objective success of SUI.^{47,53} In these studies, both approaches also showed similar results for subjective success of SUI, persistent UUI or de novo UUI. A recent Cochrane review that evaluated data of 12,113 women undergoing mid-urethral sling procedures in 81 clinical trials has demonstrated the safety and efficacy of mid-urethral slings from several different manufacturers.⁹⁴

"Mini-sling" and "single-incision" sling will not be allowed due to potential risk for higher failure rate.⁹⁵

Key aspects of the procedure will be standardized across surgeons and sites.

5.1.1 *Surgeon Certification*

To address the issue of surgeon certification for mid-urethral slings and to ensure standardized training of all surgeons, all "certified surgeons" will have performed a minimum of 20 mid-urethral slings of any type, including 5 of the mid-urethral sling allowed in MUSA that the surgeon will be using in the study. The site PI must sign off that each participating surgeon has met the criteria.

5.1.2 *Standardization of Mid-urethral Sling Procedures*

Detailed standardization of the surgical procedure will be developed and will include the following key points:

1. The participating surgeon must be present and scrubbed for key portions of the procedure. Residents and fellows may participate in procedures as is standard for each Clinical Site
2. All subjects will receive preoperative intravenous antibiotic prophylaxis. The choice of antibiotic will be determined by each surgeon.
3. Deep vein thrombosis prophylaxis is required for all participants. The choice of prophylaxis will be determined by each surgeon.
4. Any concomitant native tissue procedures must be declared prior to randomization. Per exclusion criteria, women clinically requiring anterior vaginal prolapse or apical repairs are ineligible.
5. Tensioning of the sling will be performed in a fashion to ensure that it is a tension-free technique. This can include either by placing a blunt instrument between the sling and the urethra, or by folding a small knuckle of mesh in a Babcock clamp or similar method during tensioning.

5.1.3 *Need for Postoperative Mid-urethral Sling Revision*

To address the issue of postoperative sling revision, the team developed a plan for several potential scenarios which may require the surgeon to revise the sling, detailed below. Women who undergo a sling revision will all be considered as having “additional treatment” regardless of indication. The reason for sling revision will be documented.

1. Urinary retention / incomplete bladder emptying (abnormal PVR) – An abnormal post-void residual is defined as PVR > 150 cc in this protocol (consistent with exclusion criteria). This is a known complication after mid-urethral sling. In the ESTEEM trial, the rate of sling revision was low (only one subject in each arm underwent sling revision). Similarly, Barber’s trial which included 70% women with MUI, the sling revision rate was 0-1%, which is also consistent with the TOMUS trial. For retention/incomplete emptying, the postoperative management and need for sling revision will be left up to the surgeon’s clinical judgment.
2. Worsening OAB/lower urinary tract symptoms with a normal PVR – it is possible that some women may experience worsening OAB symptoms immediately postoperatively. It is unclear from the literature in which women such symptoms may be transient and ultimately resolve once postoperative recovery is complete, or in which women it will persist and/or worsen over time. Therefore, for women with a normal PVR complaining of worsening OAB symptoms, sling revision will be deferred until 3 months postoperatively. This will provide important information about the natural course of these symptoms in the immediate postoperative period following sling. If after 3 months the patient desires sling revision due to worsening OAB symptoms, the surgeon can perform the procedure based on his/her clinical judgment. There is no evidence to support any potential harm by delaying sling revision in a woman with OAB symptoms and a normal PVR.
3. Persistent SUI symptoms – For women who have persistent SUI symptoms, sling revision/replacement can be performed after 3 months based on the surgeon’s clinical judgment.

5.2 *Botox Injection*

5.2.1 *Surgeon Certification*

To address the issue of surgeon certification for Botox intradetrusor injection and to ensure standardized training of all surgeons, all “certified surgeons” administering injections will be required to view a short instructional video demonstrating optimal techniques and detailing sites of drug injection in a standardized manner. In addition, “certified surgeons” at each site must have previously performed a total of 10 intradetrusor injection procedures.

5.2.2 *Standardization of Botox Injection Procedures*

Detailed standardization of the surgical procedure will be developed and will include the following key points:

1. The Coordinator will ensure that the subject has been instructed regarding the proper technique for clean intermittent self-catheterization (CISC) and will confirm that the subject or designated caretaker is able to perform the task.

2. Within one week prior to injection, a confirming urine pregnancy test will be performed in all premenopausal women. A urine dip to rule out infection will also be performed. If the urine dip is positive the participant will be treated for a urinary tract infection and rescheduled within 4 weeks for Botox A® injection visit.
3. The bladder will be catheterized and 50 ml of 2% lidocaine placed in the bladder and 10 ml of 2% lidocaine jelly in the urethra. The subject will be asked to lie on their left and right lateral decubitus for several minutes at a time to ensure diffuse anesthetic effect on the bladder. Cystoscopic surveillance of the bladder will be used to confirm normality.
4. Cystoscopy will be performed with a 12 or 30-degree lens and rigid or flexible scope. A 22 gauge disposable needle, which is passed through the cystoscopic channel, will be used. Approximately 100-200 ml of total fluid will be instilled during cystoscopy to allow adequate visualization of the entire bladder urothelium. Botulinum toxin A will be prepared by dissolving 100 units of botulinum toxin A into 10 ml of injectable saline. Indigo carmine or methylene blue 0.1 ml will be added to each syringe of botulinum toxin A. The treating physician will inject a total of 10 ml of the Botox A® into approximately 15 to 20 different detrusor muscle sites under direct visualization. Injections will be spread out to equally cover the posterior bladder wall and dome, but spare the bladder trigone and ureteral orifices. The anterior bladder dome will be not be injected secondary to technical difficulties associated with injecting this area cystoscopically.
5. The Coordinator will record peri-procedural events and complications. The instilled fluid will be left in the bladder after the injections are complete. The subject will remain in a post-procedure area until a spontaneous void occurs. The patient must have a spontaneous void before going home. All subjects will receive a single dose of antibiotics orally per standard of care immediately after injection and subjects will take antibiotics orally once daily for 3 days post injection.

5.2.3 *Criteria for Botox Reinjections*

Participants with persistent bothersome UUI at 3 months after their initial 100 unit Botox A injection may receive one additional injection of 100 units Botox A between 3 months and 6 months after initial injection. Eligibility for repeat Botox A injection are:

1. Persistent bothersome UUI as determined by reporting at least “moderate bother” from UUI item on UDI: “Do you experience urine leakage associated with a feeling of urgency, that is a strong sensation of needing to go to the bathroom?”
2. Continued UI bother based on the Patient Global Symptom Control (PGSC): “My current treatment is giving me adequate control of my urinary leakage”, score of ≤ 3
3. Participant desires additional treatment with Botox A
4. No UTI as determined by the health care provider on the day of the PGSC evaluation
5. PVR < 200 ml, per Botox A guidelines for UUI
6. No medical contraindication for the procedure as determined by the physician
7. Continuing to meet study inclusion/exclusion criteria (except inclusion items 2, 3, 4 7 and 8 and exclusion item 7).

A maximum of 1 additional 100 unit Botox A injection will be allowed between 3 and 6 months (total of 2 injections of 100 units Botox A). No injections will be given at an interval less than 3 months and the participant will have a post injection visit at 2 weeks (+/- 1 week) following injection.

